5.11.5 Archiving of the clinical trial master file and patients' personal data

Unless other EU laws require archiving for a longer period, the Sponsor the Site and the Principal Investigator shall archive the content of the clinical trial master file, including the relevant patients' personal data, for at least 25 years after the end of the clinical trial. However, medical records and the identification code list (i.e. the list that where the Patient ID is linked to the patients' identification data such as name and surname), including the relevant patients' personal data, shall be archived in accordance with the national laws of the country where the study is performed.

The content of the clinical trial master file shall be archived in a way that ensures that it is readily available and accessible, upon request, to the competent authorities.

Any transfer of ownership of the content of the clinical trial master file shall be documented. The new owner shall undertake the responsibilities set out in this protocol.

The Sponsor appoints the study manager as responsible person/s for archives. Access to archives shall be restricted to those individuals.

The media used to archive the content of the clinical trial master file shall be such that the content remains complete and legible throughout the period referred to in the first paragraph. Any alteration to the content of the clinical trial master file shall be traceable.

5.11.6 Data Breach

Data Breach is an incident regarding personal data security and leading to the accidental or unlawful destruction, loss, alteration, unauthorised disclosure of, or access to, personal data transmitted, stored or otherwise processed. In particular: destruction of personal data is where the data no longer exists, or no longer exists in a form that is of any use to the Site, Sponsor, CRO, Principal Investigator etc data loss is when the data may still exist, but the Site Sponsor, CRO, Principal Investigator etc has lost control or access to it, or no longer has it in its possession; damage is where personal data has been altered, corrupted, or is no longer complete; data unavailability is where, following a data incident (such as a network outage, a natural or man-made disaster, etc.), personal data become temporarily inaccessible to the Site, Sponsor, CRO, Principal Investigator etc.

Anomalous Event is an event that is not part of the standard operational scope of an infrastructure, network or service and which affects, or is likely to affect, personal data; this may include theft or loss of IT devices and other physical events (e.g. an unauthorised access to a locked storage room containing paper files with personal data), and/or electronic/IT anomalies (e.g. cyber-attacks, default or hacking of cloud services), which may in any way entail loss, unavailability, alteration, theft, copy or dissemination of personal data.

Whoever becomes aware in any way of an Anomalous Event and/or of a Data Breach (see definitions above) affecting the patients' personal data and/or personal data collected in the context of the clinical research study shall, as appropriate, immediately (and in any case no later than 24 hours from the knowledge of an Anomalous Event and/or of a Data Breach) inform the study manager, the sponsor's Data Protection Officer, who may be contacted at [REDACTED] the Site and the [name], J.D., CIPP/US, Chief Privacy Officer, Global - Office of General [REDACTED] and shall provide the following information:

- (i) Anomalous Event/Data Breach Type (e.g. data loss, unauthorized access, loss of company device, etc.);
- (ii) Person or source that first reported the Anomalous Event/Data Breach;

- (iii) Date and Time when the person who first reported the Anomalous Event/Data Breach became aware of it;
- (iv) Anomalous Event/Data Breach Date and Time (actual or presumed);
- (v) Place (specify if actual or alleged) where the Anomalous Event/Data Breach occurred ;
- (vi) Anomalous Event/Data Breach Description;
- (vii) Indicate the source of the Anomalous Event/Data Breach (e.g. I.P. source) - (if relevant);
- (viii) Indicate the affected infrastructure/system/application/cloud/software/hardware/database and their location;
- (ix) List or describe the processing/storage systems affected by the Anomalous Event/Data Breach (if relevant);
- (x) Number of data subjects involved (if known);
- (xi) Amount of allegedly breached data
- (xii) Other relevant information

Once all the above information have been provided, the Sponsor and/or the Site should have a reasonable degree of certainty that a security incident has occurred that has led to personal data being compromised.

Then, as appropriate, the Sponsor and the Site each one in its respective remit, shall manage the Data Breach in accordance with the applicable data protection regulations.

For Data Breach affecting personal data of patients enrolled within the European Union, the Sponsor and the Site autonomously or jointly -depending on the circumstances and their privacy responsibilities as defined by the Regulation 679/2016- shall:

1. collect the necessary evidence and information;
2. categorise the breach;
3. determine the risk probability and level to the rights and freedom of the concerned patients;
4. identify and put in place appropriate remedies to minimise the impact of the Data Breach;
5. determine the notification and communication duties vis à vis the competent supervisory authority and/or the concerned patients.

5.11.7 Information Notice on Personal Data Protection and Pseudonymization

Prior to patients' enrolment in the clinical research study, the Principal Investigator and/or the Site (including their personnel) shall provide each patient with adequate, law-compliant "information notices and consent forms to process personal data" as included in the ICF (or, as the case may be, through a separate, specific form) provided by the Sponsor or delegated CRO and shall collect his/her written consent to the processing of personal data according to the actual performance conditions in which the clinical research study is carried out. The Principal Investigator is responsible to archive the signed ICF in accordance with the security measures described above.

Among other things, the ICF (or the separate form) shall inform patients about:

- (i) the applicable data protection legislation;
- (ii) what kind of data shall be collected during the clinical research study listing them in detail or by category;
- (iii) the purpose of data processing (for the performance of the study and/or for pharmacovigilance purposes and/or to register new medicines) and the legal basis;
- (iv) whether granting the consent(s) to process personal data is a necessary or an optional condition to take part in the study;
- (v) the use of data for future scientific researches/secondary use of data (if any). In such a case the future scientific purposes/secondary use shall include retrospective clinical studies, clinical studies pertaining to your pathology/medical condition(s), and studies aimed at evaluating new medicine;
- (vi) the pseudonymisation procedure and scope;
- (vii) who can access patients' data and under what circumstances (Principal Investigator and site for the clinical research study conduction, Sponsor for analysis of data, regulatory authorities for registration of new medicine and/or for inspections, and the central laboratories. The complete list will be available upon request);
- (viii) the period of data retention/storage as defined in § 5.11.5 above, including the storage of the biological sample (see § 8.2.4);
- (ix) to which entities/countries outside the EU patients' data will be transmitted, (including USA and Switzerland. The complete list will be available upon request.
- (x) patients' data protection rights as defined by the EU General Data Protection Regulation 679/2016;
- (xi) Data Controllers/Data Processors and the relevant contact details;
- (xii) Sponsor's Data Protection Officer contacts [REDACTED]

(xiii) in case of genetic data processing the the possible findings, also with regard to unexpected findings that might be disclosed on account of the processing of the genetic data.

5.11.8 Genetic Data

- The collection of genetic data for performing genetic tests and screening shall be limited to the personal and family information that is absolutely indispensable for performing the study.
- The source, nature and mechanisms for samples taking and storage as defined in §8.2.4; §8.5.1 and §8.5.2.
- Without prejudice to applicable laws and regulations, except for data and results as per §5.10, the protocol shall be subject to confidentiality obligations that will assure the secrecy of the data for at least one year after the conclusion of the study.
- The measures to keep patients' identification data separated from biological materials and genetic information are reported in §5.11.4 and §5.11.5.
- Access to the premises where genetic data are stored shall be controlled by security staff and/or electronic devices also based on biometrics. Any person admitted after closing time, on whatever grounds, shall have to be identified and their data recorded.
- Preservation, use, and transportation of biological samples shall be carried out in such a manner as to also ensure their quality, integrity, availability and traceability.
- Genetic data shall be transmitted electronically by certified electronic mail after encrypting and digitally signing the information to be transmitted. Web application-based communication channels may be used if they rely on secure communication protocols and they can guarantee the digital identity of the server providing the service as well as of the client station from which the data are accessed by means of digital certificates issued by a certification authority in pursuance of the law.
- Electronically processed genetic data may be accessed provided that authentication systems are based on tokens/devices.
- Genetic data and biological samples contained in lists, registers and/or databases shall be processed with encryption techniques and/or by means of identification codes and/or any other techniques that can make them temporarily unintelligible also to the persons authorised to access them.

- In order to minimise the risks of accidental disclosure and/or unlawful/unauthorised access, patients' identities will be disclosed only when strictly necessary (e.g. to prevent a physical prejudice).
- Genetic and medical data will be processed separately from any other personal data that can identify the patients directly.
- The ICF will detail the possible findings regarding genetic data, also with regard to unexpected findings that might be disclosed as result of the test / elaboration of genetic data.
- The ICF will detail whether the data subject is allowed to limit the scope of communication of his/her genetic data and the transfer of biological samples, including their possible use for additional purposes.
- The ICF will detail the retention period of genetic data and biological samples (if different from the general retention period of other data processed in the context of the study).

5.11.9 Transfer of patients' data outside the European Union

The study performance entails transferring patients' personal data (coded data) outside the EU. To this extent, the Sponsor, the Site, the Principal investigator, the Central Laboratories, the CRO undertake to export such data in compliance with adequate safeguards/legal basis as required by the Regulation 679/2016 including the Commission Decisions, the Standard Contract Clauses, the Privacy Shield, patients' specific consent. Examples of non EU countries/entities are USA and Switzerland. The complete list will be available upon request.

5.11.10 Exercise of patients' data privacy rights

Each study patient has the right to contact the Sponsor, the Clinical Research Site, the Principal investigator, the Central Laboratories , the CRO to exercise the rights afforded to the patient by the law, including the afforded ones under articles 15 to 22 of Regulation (EU) 2016/679, namely: knowing whether or not any data referring to his/her is being processed in the context of the clinical research study; access his/her data; verify the data's content, origin, exactness, location (including, where applicable, the non EU countries where the data might be); obtain a copy of the data including their transmission to another entity indicated by the patient; ask that the data are supplemented, updated, amended; in the circumstances set forth by the law, ask that the processing of data is restricted, that data are anonymised or frozen; oppose to the processing of his/her data for legitimate reasons. Each patient has the right to lodge a complaint with his/her local supervisory

authority and/or to notify to the Data Protection Officer any use of his/her personal data the patient-regards as inappropriate.

Each study patient is free to withdraw at any time from the clinical research study. In such case, each study patient may ask the Sponsor, the Site, the Principal investigator, the Central Laboratories, the CRO to destroy/delete his/her personal data (including his/her biological (see §8.2.4) and unless they have been permanently anonymised), thus preventing any further processing or analysis of his/her data. However, data and results of tests that may have been used to determine the results of the study shall not be deleted, to avoid altering or impairing altogether the results of the study.

Specific rights in relation to the processing of genetic data applies. Please refer to §5.11.8.

If the Site, the Principal investigator, the Central Laboratories , the CRO receive a request for data privacy rights exercise, the concerned recipient shall immediately inform the Sponsor DPO by email at [REDACTED]

The request shall be fulfilled within the term set forth by the applicable privacy laws (normally 30 days). The Sponsor, the Site, the Principal investigator, the Central Laboratories, the CRO shall implement adequate organisational measures to reply to patients within the above mentioned deadline.

5.11.11 Future Research

Upon CA/EC approvals received, with patients' optional and additional consent, the Sponsor and/or the Site may use the data collected during the course of the study for further medical and scientific research purposes. These may include, for example: retrospective clinical studies; clinical studies pertaining to the patients' pathology/medical condition(s) or similar conditions; studies which compare the data of this Clinical Research Study with those from other sources to identify the factors involved in a disease; registration of new drugs.

In the context of these additional research activities, patients' data will be processed, pseudonymised and transferred abroad and may be shared with future research partners.

6. BACKGROUND INFORMATION

6.1 ANTIBODY-DRUG CONJUGATES (ADCs) IN CANCER THERAPY

At the beginning of the new century, with the approval in 1997 of the first monoclonal antibody (mAb) rituximab (anti-CD20) to treat B-cell non-Hodgkin's lymphoma (B-NHL), oncologists regarded monoclonal antibody technology as a method to avoid the toxicity associated with traditional chemotherapies and as a new tool in the direction of targeted therapy. The hope was that mAbs would have been able to bind tumor-associated antigens, leading to the elimination of targeted cells or to down-regulation of aberrantly activated pathways. This approach led to relevant improvement in management of both B-NHL and some solid tumors such as HER-2 positive breast cancer. Nevertheless, there is still an important medical need in the management of metastatic solid tumors and B-NHL with unfavorable prognostic factors and/or refractory/relapsed to standard treatments. In this context, ADCs are emerging as a novel therapeutic option in cancer treatment that looks promising for both lymphomas and solid tumors. The advantage of this class of compounds is to conjugate the selectivity of an antibody that directs the drug to the target, and the cytotoxic potency of a chemotherapy drug. The importance of these new compounds in the field of anti-cancer therapy is demonstrated by the presence of more than 40 ADCs in clinical development for various haematological malignancies and solid tumors, although so far only 2 ADCs have been approved by the FDA: T-DM1 in breast cancer and brentuximab vedotin (Adcetris®) in refractory Hodgkin Lymphoma and Anaplastic Large Cell Lymphoma (ALCL).

MEN1309 is an ADC directed against the CD205/Ly75 (DEC205) antigen, a type I transmembrane surface protein that belongs to the macrophage mannose receptor family and is expressed by dendritic cells (DCs), B and T lymphocytes, and several other tissues.

CD205/Ly75 has been reported to be suppressed in colorectal and breast cancer (1, 2) but universally expressed in both bladder carcinomas and normal urothelium (3) and induced in thymoma (4). Recently, CD205/Ly75 has been demonstrated to be hypomethylated and overexpressed in high grade epithelial ovarian cancer (5). In addition, another report showed that CD205/Ly75 expression can be important in regulating ovarian cancer invasion (6).

By means of the target discovery system Oxford Genome Anatomy Project (OGAP®), CD205/Ly75 was initially identified by proteomic analysis and was found to be highly represented in a variety of haematological malignancies and solid tumors. These data were further validated by immunohistochemistry (IHC) studies confirming that this antigen is expressed with a good prevalence in a wide array of both solid and haematological cancers.

Thus, due to (i) its known and well characterized role for antigen uptake, (ii) its role in cancer cells migration and invasion, (iii) the high frequency of expression across different cancer histotypes,

and (iv) its particular propensity to internalization, CD205/Ly75 has the potential to be a valuable antigen to be targeted by an ADC approach both for solid and haematological tumors.

MEN1309 is the result of a research project carried out by Oxford Biotherapeutics (OBT) and Menarini aimed to identify ADC targeting CD205/Ly75 antigen and inducing potent cytotoxic and antitumoral effects. A cleavable linker was selected to facilitate the exploitation of the by-stander effect (also allowing the induction of tumor reduction when the antigen is expressed in a heterogeneous manner). As toxin, a maytansine derivative, DM4, was selected in view of its remarkable cytotoxic properties due to its potent anti-tubulin action.

Extensive preclinical and translational data provided the proof of concept that MEN1309 is able to induce antitumor activity *in vitro*, in xenografts and in patient-derived xenograft (PDX) models. Furthermore, toxicological studies indicate a reasonably acceptable safety profile, allowing the definition of a safe starting dose for this first in human (FIH) clinical study.

Overall, the preclinical efficacy and safety results are very promising and warrant a phase I study to evaluate the safety and efficacy of MEN1309 in patients with CD205 positive solid tumors and NHL.

6.2 INVESTIGATIONAL MEDICINAL PRODUCT: MEN1309

6.2.1 Physical, Chemical and Pharmaceutical Properties and Formulation

MEN1309 is an ADC consisting of a recombinant humanized antibody, MBH1309, covalently linked via the lysine moiety to a maytansine derivative, DM4, a potent microtubule inhibitory agent, by the cleavable/stable linker SPDB (succinimidyl-4-(2pyridylidithio)butanoate).

MEN1309 is a sterile, clear, colorless to slightly colored solution, provided as a concentrate for solution for infusion in a single-use glass vial closed with a rubber stopper and aluminum crimp seal with a flip-off top. Each vial contains 10 mL of solution with a concentration of 5.0 mg/mL MEN1309. All excipients meet pharmacopeial standards.

The required volume of MEN1309 (5.0 mg/mL) concentrate for solution for infusion will be calculated according to the body weight of the patient, withdrawn from the vials, diluted in sterile 0.9% sodium chloride solution to a final volume of 250 mL and administered as an IV infusion.

The recommended storage conditions for MEN1309 are "2 to 8 °C, protected from light and do not freeze" The storage declaration and expiration information are provided on the label.

6.2.2 Non-Clinical Data

6.2.2.1 Non Clinical Pharmacology

6.2.2.1.1 Mechanism of Action – *in vitro*

MEN1309 is an ADC showing remarkable and specific binding to the antigen CD205/Ly75. The target antigen shows an interesting expression profile both in solid and haematological cancers. A good and fast internalization was demonstrated for the complex MBH1309/CD205, thus the conjugated toxin DM4 can be delivered inside the cell. MEN1309 shows impressive cytotoxic activity against a wide panel of human tumoral cell lines (CD205 positive) with IC_{50} in a range between 0.1-1 nM.

The affinity of the antibody to Fc γ R is quite high, nevertheless, in vitro, no Antibody-Dependent Cell-mediated Cytotoxicity (ADCC) could be demonstrated. MBH1309 is also devoid of Complement Dependent Cytotoxicity (CDC) property and of proliferative effects.

From in vitro studies, it has been demonstrated that the main mechanism of action of MEN1309 is the cytotoxicity exerted by DM4 after intracellular delivery following antibody internalization.

6.2.2.1.2 *In vivo* studies

Overall, MEN1309 showed a relevant antitumor activity against several tumor histotypes (triple-negative breast cancer [TNBC], bladder, pancreatic, and lymphomas) that express CD205/Ly75 antigen at different levels. Impressive results (in terms of complete responses according to modified Response Evaluation Criteria in Solid Tumors [mRECIST] criteria) were observed in TNBC and lymphoma xenografts. Usually the most effective dose was 5 mg/kg, but in TNBC completed responses were observed even at a dose as low as 2.5 mg/kg.

The antitumoral efficacy of MEN1309 was in general lower when the antigen was expressed in a heterogenous manner. MEN1309 has no antitumoral efficacy against CD205 negative tumors.

Moreover, a pharmacokinetic/pharmacodynamic (PK/PD) study in HAPAFII bearing mice showed that MEN1309 has a classical profile for an ADC in mouse.

6.2.2.2 Preclinical Pharmacokinetics

The pharmacokinetics of the ADC MEN1309 were evaluated in male and female cynomolgus monkeys after single intravenous doses of 3 and 5 mg/kg by intravenous infusion over 1 hour (h). The pharmacokinetic profiles observed were characterized by relatively short $t_{1/2}$ (15 to 31 h) and by extensive clearance (1.5-2.7 mL/h/kg). Such an ADC pharmacokinetic profile could be in keeping with a target-mediated drug disposition (TMDD), to be ascribed to the expression of the target antigen CD205 on some leucocyte populations in monkeys.

A compartment-model independent pharmacokinetic analysis was carried out and no dose proportionality of the exposure was found. Therefore, the pharmacokinetics of MEN1309 has to be considered non-linear.

The serum concentrations of the total antibody were comparable to those found for MEN1309, suggesting the absence of the naked antibody in the systemic circulation.

6.2.2.3 Toxokinetics (TK)

6.2.2.3.1 *Exploratory single dose intravenous toxicity study of MEN1309 in cynomolgus monkeys was performed*

The TK of the ADC MEN1309 following a single dose intravenous infusion was investigated in 2 cynomolgus monkeys (1 male and 1 female) at 3 different escalating doses (1, 3, and 5 mg/kg). An observation period of 3 weeks was considered between the different administrations. No relevant gender-related differences were observed, and no relevant differences were observed between the concentrations of MEN1309 and those of the Total Antibody.

Finally, a 3-week interval between doses was sufficient to allow a complete clearance of the drug.

6.2.2.3.2 *Toxicokinetics of MEN 1309 following single and repeated administrations in cynomolgus monkeys*

Forty cynomolgus monkeys were randomly sorted in 4 treatment groups; each group, comprising 5 males and 5 females, was intravenously treated by 1 hour infusion for 3 times every 3 weeks with placebo, 0.1, 0.3, and 1 mg/kg of MEN1309, respectively.

The pharmacokinetics were non-linear, as a consequence dose-dependent terminal half-life and clearance were observed. Furthermore, with respect to conventional IgG, shorter terminal half-life and more extensive clearance were found. This evidence is in keeping with a possible TMDD to be mainly ascribed to the expression of the target antigen CD205 on some leukocyte populations. A reduced receptor-mediated ADC uptake in leukocytes could also be responsible for the long-lasting pharmacokinetic profiles observed in some animals.

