6.2.5 Rationale for a Phase I Study and Selection of the Starting Dose

In order to identify the starting dose for the first administration in humans, nonclinical safety assessments of MEN1309 were conducted in a single relevant species, the NHP (§6.2.2.4).

The starting dose for a phase I clinical study in oncology may be defined as 1/6th of the HNSTD (8). One sixth of the MEN1309 HNSTD of 1 mg/kg equals a dose of 0.16 mg/kg. However, taking into account the novelty of the antigen and the intrinsic potency of ADCs, the Sponsor intends to have a more conservative approach applying an additional 3-fold safety factor; thus, the proposed starting dose is 0.05 mg/kg.

A PK model was developed from the PK and TK data obtained in monkeys; drug exposures in humans were simulated on a body weight allometric basis using the model parameters. A comparison of the observed exposures in monkey and the predicted exposure at the proposed starting dose in humans is provided in the Table 1:

Table 1: Comparative exposure to MEN1309 in monkey and humans

| Species | Dose definition | Dose level (mg/kg) | Infusion length (hr) | C _{max} (µg/mL) | AUC µg* hr/mL | Exposure wrt starting dose | |
|---------|-----------------|--------------------|----------------------|--------------------------|---------------|----------------------------|---------|
| | | | | | | C _{max} | AUC |
| Monkey | HNSTD | 1 | 1 | 23.61 | 438.5 | 35.2 x | 151.2 x |
| | NOAEL | 0.3 | 1 | 6.45 | 44.2 | 9.6 x | 15.2 x |
| Human | Starting | 0.05 | 3 | 0.671 | 2.9 | 1 x | 1 x |

At the proposed starting dose-level of 0.05 mg/kg in humans, the predicted exposure was a C_{max} of less than 1 µg/mL and an AUC of 2.9 µg*hr/mL. This exposure was anticipated to be 35-fold (C_{max}) and 151-fold (AUC) lower than that at the HNSTD and 10-fold (C_{max}) and 15-fold (AUC) lower than that at the NOAEL. Furthermore, at the proposed starting dose C_{max} concentration (1 µg/mL MEN1309), CD205 receptor occupancy was estimated to be approximately 20-50% on human white blood cells as determined ex-vivo by FACS.

Thus, taking together a pharmacological approach integrated with the toxicity exposure response relationship data in monkeys, the proposed starting dose in humans of 0.05 mg/kg MEN1309 was expected to provide an adequate safety margin for patients with advanced cancer.

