8. INVESTIGATIONAL PLAN

8.1 OVERALL STUDY DESIGN AND PLAN DESCRIPTION

This study is designed as an open label, multicenter, dose escalating, FIH study to be conducted in approximately 8 EU sites. Taking into consideration that only patients with CD205 positive tumors are eligible, a limited number of sites with experience in the conduction of FIH studies have been selected for trial participation and are expected to adequately contribute to the patients recruitment, in particular when the dose cohorts have to be expanded.

The study design is in agreement with the current regulatory European Medicines Agency guidelines regarding the evaluation of anticancer medicinal products in man (11, 12). The overall study design is shown in §2.1, with the plan of study procedures tabulated in § 2.2, 2.3 and 2.4.

The study will consist of 2 steps.

Step 1 aims to establish the DLT and MTD of MEN1309 in patients with CD205-positive advanced solid tumors, with dose escalation starting with 1 single patient per cohort and double dose steps per dose level (ATD) until grade ≥ 2 drug-related toxicity is observed during the DLT assessment window in the 21-day period following the first administration of MEN1309.

Upon occurrence of grade ≥ 2 drug-related toxicity, the dose escalation has to follow a modified Fibonacci sequence in which the dose increments become smaller as the dose increases (i.e., dose-increase by 67%, 50%, 40%, and 35% of the preceding doses) and a minimum of 3 patients per cohort are to be enrolled, with a minimum 7-day stagger between patients. Any cohort in which 1 patient experiences a DLT during the DLT assessment window (the 21-day period following the first administration of MEN1309) will be expanded up to 6 patients (with a minimum 24 hours stagger between the 3 additional patients).

Step 2 aims to establish the DLT and MTD of MEN1309 in patients with CD205-positive NHL following the dose escalation based upon experience gained during Step 1 in solid tumors.

Step 2 is intended to run in parallel with Step 1 but at a lower dose level, so that the cohorts of patients with NHL in Step 2 cannot exceed at any time the doses tested in solid tumors during the dose escalation.

MEN1309-01 cohorts will potentially run in parallel at the same dose level only at the time the MTD is to be confirmed in the expansion cohort of patients in Step 1 and Step 2.

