9.3.2 Pharmacokinetic Analysis

The PK analysis will be conducted on the PK population. All PK variables (i.e., serum concentrations and parameters) will be summarized by cohort using the following descriptive statistics:

- number of non-missing observations (N),
- arithmetic mean and its 95% CI, StDev, coefficient of variation (CV%), and SE,
- geometric mean (GM) and its 90% CI and GM CV%,
- minimum, median, maximum.

The concentration of MEN1309, tAb, DM4 and its metabolite S-methyl-DM4, when applicable, will be summarized for each scheduled sampling time point (see [§2.4](#)) using descriptive statistics. Individual serum concentration data versus time will be presented in a data listing and visualized as individual concentration-time plots. Additional analyses, if deemed appropriate, will be described in the statistical analysis plan.

For descriptive statistics, BLOQ concentrations at time zero, when the patient has not previously been dosed, will be set to zero. All other BLOQ values will be substituted by $\frac{1}{2}$ LLOQ value before the calculation of the summary statistics.

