number of non missing observations (N), mean, standard deviation (SD), geometric mean and its 95% confidence interval (CI), minimum, median, maximum and coefficient of variation (CV %).

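### The protocol calls MEN1309 pharmacokinetics non-linear, but neither document pre-specifies an estimate of how exposure scales with dose; a pooled power model would be a cheap improvement

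*Protocol*

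**What the plan says.** Protocol 6.2.2.2, on single doses of 3 and 5 mg/kg in monkeys, reports that "no dose proportionality of the exposure was found" and concludes: "Therefore, the pharmacokinetics of MEN1309 has to be considered non-linear". Protocol 6.2.2.3.2 repeats the finding for 0.1 to 1 mg/kg: "The pharmacokinetics were non-linear, as a consequence dose-dependent terminal half-life and clearance were observed". It suggests target-mediated disposition through CD205 on leukocytes as a possible cause.

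Step 1 runs "dose escalation starting with 1 single patient per cohort and double dose steps per dose level" until a grade 2 or higher drug-related toxicity (Protocol 8.1). Protocol 6.3 identifies 0.80 mg/kg as Cohort 5 and counts six cohorts up to 1.60 mg/kg. Protocol 6.2.3 says that the 1.60 mg/kg cohort was expanded to six patients.

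The analysis rule in Protocol 9.3.2 is: "All PK variables (i.e., serum concentrations and parameters) will be summarized by cohort using the following descriptive statistics". The list covers the arithmetic mean with 95% CI, SD, CV%, SE, the geometric mean with 90% CI, and the range. Individual concentrations are listed and plotted. Further PK analyses are left to the SAP, if thought suitable.

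SAP 6.1.1.2 gives concentrations by time point and, for parameters, "number of non missing observations (N), mean, standard deviation (SD), geometric mean and its 95% confidence interval (CI", followed by range, median and CV%. It adds no further PK analysis. Assessing the PK profile after single and repeated doses is a secondary objective in both documents (Protocol 7.2, SAP section 2).

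**The concern.** For a drug whose clearance is expected to change with dose, how exposure scales with dose is a central part of the PK profile. By-cohort summaries do not answer that question. In the one-patient cohorts there is no spread or interval to report. The larger cohorts have intervals, but each describes one dose and not the trend across doses. A summary pooled over all doses, which Protocol 9.3.1 would also produce, averages AUC across a wide dose range and says nothing about the slope.

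At stake is a statement with stated uncertainty about whether human exposure rises faster than dose. The planned samples can support one. Under Protocol 9.5, an analysis that is not pre-specified and is run after data lock counts as additional or exploratory, so the model should be written down before lock.

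**Working it through.** **1. Cohorts.** Doubling from 0.05 mg/kg gives 0.05, 0.10, 0.20, 0.40, 0.80, 1.60. This reproduces 0.80 as Cohort 5 and 1.60 as Cohort 6. The next levels are 1.60 × 1.5 = 2.40 (Protocol 6.2.3) and 2.40 × 1.4 = 3.36 mg/kg, the top Step 1 dose in SAP section 1. By design, five of these eight levels have one patient.

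**2. Protocol Table 1 (section 6.2.5).** Its ratios to the human starting dose reproduce:
- 1 mg/kg in monkey: 23.61/0.671 = 35.2 (Cmax); 438.5/2.9 = 151.2 (AUC).
- 0.3 mg/kg in monkey: 6.45/0.671 = 9.6; 44.2/2.9 = 15.2.

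**3. Size of the non-linearity in monkeys, from the same table.**
- Dose ratio 1/0.3 = 3.33; AUC ratio 438.5/44.2 = 9.92; slope ln 9.92 / ln 3.33 = 2.295/1.204 = 1.91.
- Cmax ratio 23.61/6.45 = 3.66; slope 1.298/1.204 = 1.08.
- Dose/AUC: 300/44.2 = 6.79 mL/h/kg at 0.3 mg/kg; 1000/438.5 = 2.28 mL/h/kg at 1 mg/kg. This treats the tabulated AUC as complete, which the table does not state.

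**4. What exists at n = 1.** Mean, geometric mean, median, minimum and maximum all equal the single value. The SD has n − 1 = 0 degrees of freedom, so SD, SE, CV% and every confidence interval are undefined.

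**5. What a pooled power model would give.** Model: ln AUC = a + b ln dose. With s = √ln(1 + CV²), SE(b) = s/√Sxx, and the 90% CI half-width is t(0.95, N − 2) × SE(b). The documents give no between-patient CV, so 40% is assumed (range 30–60%), giving s = 0.385 (0.294–0.555).

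| Step 1 patients (assumed) | N | Sxx | t | Half-width at CV 40% (30–60%) |
|---|---|---|---|---|
| 1,1,1,1,1,6 up to 1.60 mg/kg | 11 | 16.60 | 1.833 | 0.17 (0.13–0.25) |
| plus 3 at 2.40 and 6 at 3.36 mg/kg | 20 | 29.10 | 1.734 | 0.12 (0.09–0.18) |

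For example, at N = 20: 1.734 × 0.385/√29.10 = 1.734 × 0.0714 = 0.12. Neither row includes the TNBC expansion patients. If all 25 were added at 2.40 or at 3.36 mg/kg, the half-width at CV 40% would be about 0.11 or 0.10.

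**6. By-cohort comparison.** At n = 3 and CV 40%, the 90% CI of a geometric mean is the estimate multiplied and divided by exp(2.920 × 0.385/√3) = 1.91. At 95% the factor is exp(4.303 × 0.385/√3) = 2.60. The first level is the protocol's and the second the SAP's, so the mismatch visibly changes the reported interval.

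**7. Sampling.** Day 8 and Day 15 PK samples are taken only at 0.80 mg/kg and above (Protocol 2.4 and 8.5.3). Below that, scheduled Cycle 1 sampling ends 72 hours after the end of infusion. AUC(0–∞) and clearance therefore rest on different follow-up on the two sides of 0.80 mg/kg.

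**The case against.** The strongest reply is that this is a descriptive first-in-human trial whose PK objective does not name dose proportionality. The protocol derives clearance, AUC and half-life for each patient and lists and plots individual concentrations. The synopsis gives the PK statistics only where suitable, so undefined ones can simply be left out. The cohort review committee sees PK data before each escalation. Additional analyses are permitted, and a regression could be added later as exploratory.

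Much of this stands. The missing SDs at n = 1 are a limit of display and not an error, and a trend in individual values can be seen by eye. None of it supplies a pre-specified estimate. The optional PK/PD work in Protocol 8.5.3 relates exposure to clinical activity, not to dose.

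Three stronger readings are tempting and not supported:
- *Non-linearity can never be estimated, or no summary exists at n = 1.* Means and individual values exist, and further analysis is allowed.
- *The change in clearance lies below about 1 mg/kg, exactly where cohorts have one patient.* Table 1 shows a steep change from 0.3 to 1 mg/kg, but Protocol 6.2.2.2 reports lack of proportionality in the 3 and 5 mg/kg study. Monkey doses also do not carry over directly to patients.
- *Leukocyte CD205 is the established driver of clearance and must enter the model.* The protocol calls the mechanism only possible.

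**Conclusion.** The point holds as a cheap improvement: no estimate of the dose–exposure relationship is pre-specified for a drug the protocol itself describes as non-linear. This does not make the trial or its MTD rules invalid, and it concerns a secondary objective.

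A single pooled slope would be estimated to within about ±0.12 (±0.09 to ±0.18). That is narrow enough to separate a slope near the monkey value of 1.91 from 1, if the human slope is of that order. The figure assumes the cohort sizes and CV shown above and a log-linear relationship with log-normal errors. One patient per accelerated cohort is the design size: the documents do not give actual counts, and replacements could raise them.

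**What to change.** In Protocol 9.3.2 and the PK part of SAP 6.1.1.2:

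- Pre-specify a regression of ln AUC and ln Cmax in Cycle 1 on ln of the dose actually given. Include all Step 1 patients in the PK population, expansion cohort included, and report each slope with its 90% CI. A separate model for ln clearance adds little, because clearance is dose divided by AUC(0–∞).
- Use an AUC over a window sampled at every dose, for example to 72 hours after the end of infusion, as the main or a sensitivity analysis, with AUC(0–∞) beside it.
- Check curvature as exploratory, for example with a quadratic term in ln dose. Do not fix a change of slope at 0.80 mg/kg, where it would be confounded with the longer sampling.
- Treat baseline CD205 by flow cytometry as an exploratory covariate only.
- For cohorts with fewer than three patients, list individual parameter values in place of SDs and CIs.
- State one confidence level for the geometric mean; it is 90% in the protocol and 95% in the SAP.

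The cost is wording and one regression per parameter, with no extra patients or samples. The downside is reliance on a log-normal, log-linear approximation over a dose range of 3.36/0.05 = 67-fold. The curvature check is there to test it.
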